8.3.1.1. Reporting SAEs to Pfizer Safety

All SAEs occurring in a participant during the active collection period as described in Section 8.3.1 are reported to Pfizer Safety on the Vaccine SAE Reporting Form immediately upon awareness and under no circumstance should this exceed 24 hours, as indicated in Appendix 3. The investigator will submit any updated SAE data to the sponsor within 24 hours of it being available.

8.3.1.2. Recording Nonserious AEs and SAEs on the CRF

All nonserious AEs and SAEs occurring in a participant during the active collection period, which begins after obtaining informed consent as described in Section 8.3.1, will be recorded on the AE section of the CRF.

The investigator is to record on the CRF all directly observed and all spontaneously reported AEs and SAEs reported by the participant.

8.3.2. Method of Detecting AEs and SAEs

The method of recording, evaluating, and assessing causality of AEs and SAEs and the procedures for completing and transmitting SAE reports are provided in Appendix 3.

Care will be taken not to introduce bias when detecting AEs and/or SAEs. Open-ended and nonleading verbal questioning of the participant is the preferred method to inquire about AE occurrences.

8.3.3. Follow-Up of AEs and SAEs

After the initial AE or SAE report, the investigator is required to proactively follow each participant at subsequent visits/contacts. For each event, the investigator must pursue and obtain adequate information until resolution, stabilization, the event is otherwise explained, or the participant is lost to follow-up (as defined in Section 7.3).

In general, follow-up information will include a description of the event in sufficient detail to allow for a complete medical assessment of the case and independent determination of possible causality. Any information relevant to the event, such as concomitant medications and illnesses, must be provided. In the case of a participant death, a summary of available autopsy findings must be submitted as soon as possible to Pfizer Safety.

Further information on follow-up procedures is given in Appendix 3.

8.3.4. Regulatory Reporting Requirements for SAEs

Prompt notification by the investigator to the sponsor of an SAE is essential so that legal obligations and ethical responsibilities toward the safety of participants and the safety of a study intervention under clinical investigation are met.

The sponsor has a legal responsibility to notify both the local regulatory authority and other regulatory agencies about the safety of a study intervention under clinical investigation. The sponsor will comply with country-specific regulatory requirements relating to safety reporting to the regulatory authority, IRBs/ECs, and investigators.

Investigator safety reports must be prepared for SUSARs according to local regulatory requirements and sponsor policy and forwarded to investigators as necessary.

An investigator who receives SUSARs or other specific safety information (eg, summary or listing of SAEs) from the sponsor will review and then file it along with the SRSD(s) for the study and will notify the IRB/EC, if appropriate according to local requirements.

8.3.5. Environmental Exposure, Exposure During Pregnancy or Breastfeeding, and Occupational Exposure

Environmental exposure occurs when a person not enrolled in the study as a participant receives unplanned direct contact with or exposure to the study intervention. Such exposure may or may not lead to the occurrence of an AE or SAE. Persons at risk for environmental exposure include healthcare providers, family members, and others who may be exposed. An environmental exposure may include exposure during pregnancy, exposure during breastfeeding, and occupational exposure.

Any such exposure to the study intervention under study are reportable to Pfizer Safety within 24 hours of investigator awareness.

8.3.5.1. Exposure During Pregnancy

An EDP occurs if:

- A female participant is found to be pregnant while receiving or after discontinuing study intervention.
- A male participant who is receiving or has discontinued study intervention exposes a female partner prior to or around the time of conception.
- A female is found to be pregnant while being exposed or having been exposed to study intervention due to environmental exposure. Below are examples of environmental EDP:
 - A female family member or healthcare provider reports that she is pregnant after having been exposed to the study intervention by inhalation or skin contact.
 - A male family member or healthcare provider who has been exposed to the study intervention by inhalation or skin contact then exposes his female partner prior to or around the time of conception.
- The investigator must report EDP to Pfizer Safety within 24 hours of the investigator's awareness, irrespective of whether an SAE has occurred. The initial information submitted should include the anticipated date of delivery (see below for information related to termination of pregnancy).
- If EDP occurs in a participant or a participant's partner, the investigator must report this information to Pfizer Safety on the Vaccine SAE Reporting Form and an EDP Supplemental Form, regardless of whether an SAE has occurred. Details of the pregnancy will be collected after the start of study intervention and until 28 days after the last dose of study intervention. Beyond 28 days after the last dose of study intervention, any pregnancy that occurs will not be considered EDP for this study.
- If EDP occurs in the setting of environmental exposure, the investigator must report information to Pfizer Safety using the Vaccine SAE Reporting Form and EDP Supplemental Form. Since the exposure information does not pertain to the participant enrolled in the study, the information is not recorded on a CRF; however, a copy of the completed Vaccine SAE Reporting Form is maintained in the investigator site file.

Follow-up is conducted to obtain general information on the pregnancy and its outcome for all EDP reports with an unknown outcome. The investigator will follow the pregnancy until completion (or until pregnancy termination) and notify Pfizer Safety of the outcome as a follow-up to the initial EDP Supplemental Form. In the case of a live birth, the structural integrity of the neonate can be assessed at the time of birth. In the event of a termination, the reason(s) for termination should be specified and, if clinically possible, the structural

integrity of the terminated fetus should be assessed by gross visual inspection (unless preprocedure test findings are conclusive for a congenital anomaly and the findings are reported).

Abnormal pregnancy outcomes are considered SAEs. If the outcome of the pregnancy meets the criteria for an SAE (ie, ectopic pregnancy, spontaneous abortion, intrauterine fetal demise, neonatal death, or congenital anomaly), the investigator should follow the procedures for reporting SAEs. Additional information about pregnancy outcomes that are reported to Pfizer Safety as SAEs follows:

- Spontaneous abortion including miscarriage and missed abortion;
- Neonatal deaths that occur within 1 month of birth should be reported, without regard to causality, as SAEs. In addition, infant deaths after 1 month should be reported as SAEs when the investigator assesses the infant death as related or possibly related to exposure to the study intervention.

Additional information regarding the EDP may be requested by the sponsor. Further follow-up of birth outcomes will be handled on a case-by-case basis (eg, follow-up on preterm infants to identify developmental delays). In the case of paternal exposure, the investigator will provide the participant with the Pregnant Partner Release of Information Form to deliver to his partner. The investigator must document in the source documents that the participant was given the Pregnant Partner Release of Information Form to provide to his partner.

8.3.5.2. Exposure During Breastfeeding

An exposure during breastfeeding occurs if:

- A female participant is found to be breastfeeding while receiving or after discontinuing study intervention.
- A female is found to be breastfeeding while being exposed or having been exposed to study intervention (ie, environmental exposure). An example of environmental exposure during breastfeeding is a female family member or healthcare provider who reports that she is breastfeeding after having been exposed to the study intervention by inhalation or skin contact.

The investigator must report exposure during breastfeeding to Pfizer Safety within 24 hours of the investigator's awareness, irrespective of whether an SAE has occurred. The information must be reported using the Vaccine SAE Reporting Form. When exposure during breastfeeding occurs in the setting of environmental exposure, the exposure information does not pertain to the participant enrolled in the study, so the information is not recorded on a CRF. However, a copy of the completed Vaccine SAE Reporting Form is maintained in the investigator site file.

An exposure during breastfeeding report is not created when a Pfizer drug specifically approved for use in breastfeeding women (eg, vitamins) is administered in accord with authorized use. However, if the infant experiences an SAE associated with such a drug, the SAE is reported together with the exposure during breastfeeding.

8.3.5.3. Occupational Exposure

The investigator must report any instance of occupational exposure to Pfizer Safety within 24 hours of the investigator's awareness using the Vaccine SAE Reporting Form, regardless of whether there is an associated SAE. Since the information about the occupational exposure does not pertain to a participant enrolled in the study, the information is not recorded on a CRF; however, a copy of the completed Vaccine SAE Reporting Form must be maintained in the investigator site file.

8.3.6. Cardiovascular and Death Events

Not applicable.

8.3.7. Disease-Related Events and/or Disease-Related Outcomes Not Qualifying as AEs or SAEs

8.3.7.1. Substudies Including a Potential COVID-19 Illness Visit

The following substudies include a potential COVID-19 illness visit: Substudies A, D, E, and F.

Only for substudies including a potential COVID-19 illness visit, potential COVID-19 illnesses and their sequelae that are consistent with the clinical endpoint definition should not be recorded as AEs. These data will be captured as efficacy assessment data only on the relevant pages of the CRF, as these are expected endpoints.

Potential COVID-19 illnesses and their sequelae will not be reported according to the standard process for expedited reporting of SAEs, even though the event may meet the definition of an SAE. These events will be recorded on the COVID-19 illness pages in the participant's CRF within 1 day.

NOTE: However, if either of the following conditions applies, then the event must be recorded and reported as an SAE (instead of a disease-related event):

The event is, in the investigator's opinion, of greater intensity, frequency, or duration than expected for the individual participant.

OR

The investigator considers that there is a reasonable possibility that the event was related to study intervention.

Potential COVID-19 illness events and their sequelae will be reviewed by a group of internal blinded case reviewers. Any SAE that is determined by the internal case reviewers NOT to meet endpoint criteria is reported back to the investigator site of incidence. The investigator must report the SAE to Pfizer Safety within 24 hours of being made aware that the SAE did not meet endpoint criteria. The investigator's SAE awareness date is the date on which the investigator site of incidence receives the SAE back from the internal case reviewers.

8.3.7.2. Substudies NOT Including a Potential COVID-19 Illness Visit

For substudies not including a potential COVID-19 illness visit, confirmed COVID-19 diagnoses will be considered AESIs (Section 8.3.8).

8.3.8. Adverse Events of Special Interest

The following events are considered AESIs:

 A confirmed diagnosis of myocarditis or pericarditis. See Section 10.7.8.5.9 for Substudy A, Section 10.8.8.3.6 for Substudy B, Section 10.9.8.5 for Substudy C, Section 10.10.8.6.7 for Substudy D, Section 10.11.8.6.12 for Substudy E, and Section 10.12.8.5.10 for Substudy F for additional procedures for monitoring of potential myocarditis or pericarditis.

8.3.8.1. Substudies NOT Including a Potential COVID-19 Illness Visit

This section provides information on AESIs that may be detected during the study:

 Confirmed COVID-19 diagnosis (clinical signs/symptoms and positive SARS-CoV-2 NAAT test)

AESIs are examined as part of routine safety data review procedures throughout the clinical trial and as part of signal detection processes.

All AESIs must be reported as an AE or SAE following the procedures described in Sections 8.3.1 through Section 8.3.4. An AESI is to be recorded as an AE or SAE on the CRF. In addition, an AESI that is also an SAE must be reported using the Vaccine SAE Reporting Form.

8.3.8.2. Lack of Efficacy

The investigator must report signs, symptoms, and/or clinical sequelae resulting from lack of efficacy. Lack of efficacy or failure of expected pharmacological action is reportable to Pfizer Safety only if associated with an SAE.

8.3.9. Medical Device Deficiencies

Not applicable.

8.3.10. Medication Errors

Medication errors may result from the administration or consumption of the study intervention by the wrong participant, or at the wrong time, or at the wrong dosage strength.

Exposures to the study intervention under study may occur in clinical trial settings, such as medication errors.

| Safety Event | Recorded on the CRF | Reported on the Vaccine SAE Reporting Form to Pfizer Safety Within 24 Hours of Awareness |
|-------------------|---|--|
| Medication errors | All (regardless of whether associated with an AE) | Only if associated with an SAE |

Medication errors include:

- Medication errors involving participant exposure to the study intervention;
- Potential medication errors or uses outside of what is foreseen in the protocol that do or do not involve the study participant.
- The administration of expired study intervention;
- The administration of an incorrect study intervention;
- The administration of an incorrect dosage;
- The administration of study intervention that has undergone temperature excursion from the specified storage range, unless it is determined by the sponsor that the study intervention under question is acceptable for use.

Such medication errors occurring to a study participant are to be captured on the medication error page of the CRF, which is a specific version of the AE page.

In the event of a medication dosing error, the sponsor should be notified within 24 hours.

Whether or not the medication error is accompanied by an AE, as determined by the investigator, the medication error is recorded on the medication error page of the CRF and, if applicable, any associated AE(s), serious and nonserious, are recorded on the AE page of the CRF.

Medication errors should be reported to Pfizer Safety within 24 hours on a Vaccine SAE Reporting Form **only when associated with an SAE**.

8.4. Pharmacokinetics

Pharmacokinetic parameters are not evaluated in this study.

8.5. Genetics

8.5.1. Specified Genetics

For Substudies A, B, C, and F, genetics (specified analyses) are not evaluated.

For Substudies D and E, please see Section 10.16.

8.6. Biomarkers

Biomarkers are not evaluated in this study.

8.7. Immunogenicity Assessments

Immunogenicity assessments are described in Section 8.1.

8.8. Health Economics

Health economics/medical resource utilization and health economics parameters are not evaluated in this study.

9. STATISTICAL CONSIDERATIONS

Methodology for summary and statistical analyses of the data collected in this study is outlined here and further detailed in a SAP, which will be maintained by the sponsor. The SAP may modify what is outlined in the protocol where appropriate; however, any major modifications of the primary endpoint definitions or their analyses will also be reflected in a protocol amendment.

9.1. Statistical Hypotheses

9.1.1. Estimands

For estimands, refer to the respective appendix for each substudy. For Substudy A, refer to Section 10.7.3. For Substudy B, refer to Section 10.8.3. For Substudy C, refer to Section 10.9.3. For Substudy D, refer to Section 10.10.3. For Substudy E, refer to Section 10.11.3. For Substudy F, refer to Section 10.12.3.

9.1.2. Statistical Hypotheses

For Substudy A, refer to Section 10.7.9.1.2 for hypotheses.

For Substudy B, refer to Section 10.8.9.1.2 for hypotheses.

For Substudy C, refer to Section 10.9.9.1.2 for hypotheses.

For Substudy D, refer to Section 10.10.9.1.2 for hypotheses.

For Substudy E, refer to Section 10.11.9.1.2 for hypotheses.

For Substudy F, refer to Section 10.12.9.1.2 for hypotheses.

9.1.3. Multiplicity Adjustments

For Substudy A, refer to Section 10.7.9.1.3 for multiplicity adjustments.

For Substudy B, refer to Section 10.8.9.1.3 for multiplicity adjustments.

For Substudy C, refer to Section 10.9.9.1.3 for multiplicity adjustments.

For Substudy D, refer to Section 10.10.9.1.3 for multiplicity adjustments.

For Substudy E, refer to Section 10.11.9.1.3 for multiplicity adjustments.

For Substudy F, refer to Section 10.12.9.1.3 for multiplicity adjustments.

9.2. Analysis Sets

For analysis sets, refer to the respective appendix for each substudy.

For Substudy A, refer to Section 10.7.9.2.

For Substudy B, refer to Section 10.8.9.2.

For Substudy C, refer to Section 10.9.9.2.

For Substudy D, refer to Section 10.10.9.2.

For Substudy E, refer to Section 10.11.9.2.

For Substudy F, refer to Section 10.12.9.2.

9.3. Statistical Analyses

The SAP will be developed and finalized for each substudy before any analyses are performed and will describe the analyses and procedures for accounting for missing, unused, and spurious data. This section is a summary of the general considerations of statistical analyses.

Refer to each substudy appendix for description of the statistical analyses for primary, secondary, and/or exploratory endpoints. For Substudy A, refer to Section 10.7.9.3. For Substudy B, refer to Section 10.8.9.3. For Substudy C, refer to Section 10.9.9.3. For Substudy D, refer to Section 10.10.9.3. For Substudy E, refer to Section 10.11.9.3. For Substudy F, refer to Section 10.12.9.3.

9.3.1. General Considerations

Each substudy will be reported separately.

CIs for all endpoints in the statistical analysis will be presented as 2-sided at the 95% level unless specified otherwise.

The safety analyses are based on the safety population. Participants will be summarized by vaccine group according to the study interventions they received. Missing reactogenicity e-diary data will not be imputed; missing AE dates will be handled according to the Pfizer safety rules.

For all the immunogenicity endpoints, the analysis will be based on the evaluable immunogenicity population. An additional analysis may be performed based on the all-available immunogenicity populations if there is a large enough difference in sample size between the all-available immunogenicity population and the evaluable immunogenicity population. Participants will be summarized according to the vaccine group to which they were randomized. Missing serology data will not be imputed.

The evaluable efficacy population will be the primary analysis population for all efficacy analyses. Additional analyses based on the all-available efficacy (mITT) population will be performed. Participants will be summarized according to the vaccine group to which they were randomized. Missing laboratory results will not be imputed.

9.3.1.1. Analyses for Binary Data

Descriptive statistics for categorical variables (eg, proportions) are the percentage (%), the numerator (n) and the denominator (N) used in the percentage calculation, and the 95% CIs where applicable.

The exact 95% CI for binary endpoints for each group will be computed using the F distribution (Clopper-Pearson method). The 95% CI for the between-group difference for binary endpoints will be calculated using the Miettinen and Nurminen method.

The 3-tier approach may be used to summarize AEs for certain substudies (refer to each substudy for specification). For both Tier 1 (if any are identified during the study) and Tier 2 events, a 95% CI for the between-group difference in proportions will be calculated based on the Miettinen and Nurminen method. In addition, for Tier 1 events (if any), the asymptotic p-values will also be presented for the difference in proportions, based on the same test statistic and under the assumption that the test statistic is asymptotically normally distributed. For Tier 3 events, counts and percentages for each vaccine group will be provided.

9.3.1.2. Analyses for Continuous Data

Unless otherwise stated, descriptive statistics for continuous variables are n, mean, median, standard deviation, minimum, and maximum.

9.3.1.2.1. Geometric Means

The geometric means will be calculated as the mean of the assay results after making the logarithm transformation and then exponentiating the mean to express results on the original scale. Two-sided 95% CIs will be obtained by taking log transforms of assay results, calculating the 95% CI with reference to Student's t-distribution, and then exponentiating the confidence limits.

9.3.1.2.2. Geometric Mean Fold Rises

GMFRs are defined as ratios of the results after vaccination to the results before vaccination. GMFRs are limited to participants with nonmissing values at both time points.

GMFRs will be calculated as the mean of the difference of logarithmically transformed assay results (later time point minus earlier time point) and exponentiating the mean. The associated 2-sided 95% CIs will be obtained by constructing CIs using Student's t-distribution for the mean difference on the logarithm scale and exponentiating the confidence limits.

9.3.1.2.3. Geometric Mean Ratios

The GMR will be calculated as the mean of the difference of logarithmically transformed assay results and exponentiating the mean. Two-sided CIs will be obtained by calculating CIs using Student's t-distribution for the mean difference of the logarithmically transformed assay results and exponentiating the confidence limits.

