Participants in Cohort 1 will have completed a 2-dose primary series of BNT162b2 (30-µg doses), with their last dose 90 to 240 days prior to enrollment. Approximately 615 participants will be randomized at a ratio of 1:1:1 either to receive 1 dose (third) of BNT162b2 OMI, 2 doses (third and fourth) of BNT162b2 OMI, 4 weeks apart, or 1 dose (third) of BNT162b2. Randomization will be stratified by age (stratified as 18-30 and 31-55 years of age). Participants in Cohort 1 will remain blinded to whether they will be receiving a fourth dose through 1 month after their first dose, but the investigator and sponsor will not be blinded.

Participants in Cohort 2 will be enrolled from Study C4591001 and C4591031 Substudy A and will have completed a 2-dose primary series and received a single booster (third) dose of BNT162b2, with their last dose 90 to 180 days prior to randomization. Approximately 600 participants will be randomized at a ratio of 1:1 to receive a fourth dose of either BNT162b2 or BNT162b2 OMI at Visit 401. Participants will be offered a dose of BNT162b2 OMI at Visit 404 (3-month follow-up). Randomization will be stratified by age (stratified as 18-30 and 31-55 years of age). Cohort 2 will be observer-blinded.

In Cohort 3, 205 participants 18 through 55 years of age who are COVID-19 vaccine—naïve and have not experienced COVID-19 will be enrolled to receive 2 doses (primary series) of BNT162b2 OMI, 3 weeks apart, with a dose of BNT162b2 approximately 5 months (150 days) later. If participants do not consent to receive BNT162b2 as a third dose, they will not receive a third dose. No participants should receive BNT162b2 OMI as a third dose.

Table 1 details the number of participants by cohort and group, their prior BNT162b2 experience, the vaccine that will be administered, and the number of doses administered as part of Substudy D.

Table 1. Total Number of Participants by Cohort

| Cohort | Group | Prior BNT162b2 Experience | Vaccine | Number of Doses Administered as Part of Substudy D | Total Number of Participants |
|----------|----------|---------------------------------|--------------|---|---------------------------------|
| Cohort 1 | Group 1 | 2 Doses | BNT162b2 OMI | 1 | 205 |
| | Group 2 | 2 Doses | BNT162b2 OMI | 2 | 205 |
| | Group 2b | 2 Doses | BNT162b2 | 1 | 205 |

| Table 1. I dial Number of Latticipants by Conor | Table 1. | Total Number of Participants by Cohort |
|---|----------|---|
|---|----------|---|

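### The master GMR definition does not describe a ratio between independent randomised groups, and it uses neither the pre-dose titre nor the age stratum

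*Protocol*

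**What the plan says.** Section 9.3.1.2.3 of the protocol defines the GMR in two sentences. The estimate: "The GMR will be calculated as the mean of the difference of logarithmically transformed assay results and exponentiating the mean". The interval is obtained by "calculating CIs using Student's t-distribution for the mean difference of the logarithmically transformed assay results". No pairing, model, covariate or stratum is named. Section 9.3.1 sets the level: "CIs for all endpoints in the statistical analysis will be presented as 2-sided at the 95% level unless specified otherwise".

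The section just before it, 9.3.1.2.2, uses nearly the same wording for the within-participant fold rise, but there it states the pairing: "GMFRs will be calculated as the mean of the difference of logarithmically transformed assay results (later time point minus earlier time point". It also restricts the calculation to participants with values at both time points.

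Section 9.3 describes itself as a summary and sends the reader on: "Refer to each substudy appendix for description of the statistical analyses for primary, secondary, and/or exploratory endpoints". Section 9 adds: "The SAP may modify what is outlined in the protocol where appropriate", with major changes to primary endpoint analyses also to appear in a protocol amendment.

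On design, the Synopsis says of Substudy D Cohort 2: "Approximately 600 participants will be randomized at a ratio of 1:1 to receive a fourth dose". For Cohorts 1 and 2 it says: "Randomization will be stratified by age (stratified as 18-30 and 31-55 years of age". The schedules of activities in Sections 10.10.1.3.1 and 10.10.1.3.2 list an immunogenicity blood sample at Visit 401, the first vaccination visit, ahead of administration of the study intervention.

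**The concern.** A mean of differences needs pairs. Two strains measured in one serum form a pair, and so do two visits of one participant. Participants randomised to two different vaccines do not. For them the quantity is the difference between two group means on the log scale, each computed as in Section 9.3.1.2.1. One paragraph is made to serve both cases, and it leaves open whether the Student t interval is one-sample or two-sample.

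The second issue is efficiency. Before the first study dose the trial already holds a blood sample and, in Substudy D Cohorts 1 and 2, an age stratum used in randomisation. Participants enter with different intervals since their last dose (90 to 240 days in Cohort 1, 90 to 180 days in Cohort 2), so baseline titres can be expected to differ. If baseline titre predicts post-dose titre, an analysis without it leaves explainable variance in the error term. What is at stake is the width of the interval for randomised between-group GMRs, not their validity.

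**Working it through.** **Plan's own figure.** The available text gives no standard deviation, correlation, interval width or power for a GMR, so there is nothing to reproduce.

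**Where the definition could apply.** The substudy analysis sections, set side by side:

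- Substudy A (10.7.9.3): vaccine efficacy from an incidence rate ratio. No GMR.
- Substudy B (10.8.9.3): troponin and safety percentages. No GMR.
- Substudy C (10.9.9.3): GMT, GMFR and seroresponse per group, descriptive, each age group analysed separately. No between-group GMR.
- Substudies D, E and F (10.10.9, 10.11.9, 10.12.9): not in the text available here, which stops in Section 10.10.2.1. Whether they rely on Section 9.3.1.2.3 or define their own model could not be checked.

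**Inputs.** About 300 per group in Substudy D Cohort 2 (600 randomised 1:1, Synopsis). About 100 per group for the Cohort 1 sample named in the amendment 12 summary of changes. Two-sided 95% level (Section 9.3.1). Assumed: standard deviation s of ln titre = 1.0, with 0.8 and 1.2 as the range; r from 0 to 0.6.

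**Formulas**, half-widths on the ln scale with n per group:

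- Unadjusted: h0 = t(2n-2) × s × sqrt(2/n)
- Adjusted for baseline: h1 = t(2n-3) × s × sqrt(1 - r²) × sqrt(2/n) × sqrt(1 + 1/(2n-4))

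In large samples h1/h0 = sqrt(1 - r²), which does not depend on s.

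**Results.** The confidence limits are the GMR multiplied and divided by exp(h).

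| r | sqrt(1 - r²) | CI narrower by | exp(h1), n = 300 | exp(h1), n = 100 |
|---|---|---|---|---|
| 0 | 1.000 | 0% | 1.174 | 1.323 |
| 0.3 | 0.954 | 5% | 1.165 | 1.306 |
| 0.5 | 0.866 | 13% | 1.149 | 1.274 |
| 0.6 | 0.800 | 20% | 1.137 | 1.251 |

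The unadjusted factors exp(h0) are 1.174 (n = 300) and 1.322 (n = 100). With n = 300 and r = 0.5, the factor goes from 1.137 to 1.118 if s = 0.8, and from 1.212 to 1.182 if s = 1.2.

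**Simulation check.** Least-squares fits with n = 100 per group and 1000 runs per r gave mean width ratios of 1.003, 0.957 and 0.867 at r = 0, 0.3 and 0.5. At r = 0 the adjusted interval was wider in 80% of runs, by about 0.3% on average. That is the price of adjusting when baseline carries no information.

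**Age stratum.** Its further contribution is not quantified, because no figure for age-related variation in titre is available.

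**The case against.** The strongest case against has four parts.

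First, Section 9.3 is a general summary; endpoint methods sit in the appendices and the SAP, and covariate choice is ordinary content for those. This stands in part: an appendix for D, E or F may already specify an adjusted model, and then only the wording needs repair. It does not dispose of the point, because Section 9.3.1.2.3 does not stay silent. It states a method, and leave to modify that method is not a modification.

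Second, an unadjusted randomised comparison is valid, and its interval already allows for chance baseline imbalance. This stands in full. A reader might infer that the GMR would be biased; it would not be.

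Third, the wording is loose rather than wrong, since it suits a within-participant ratio. That is fair. A reader might also infer that a paired interval would be run on independent arms and come out too narrow. With no pairs that calculation cannot be done, so the fault is an incomplete definition with no shown effect on a result.

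Fourth, the gain rests on an assumed r. This stands, and r = 0 gives nothing. One can build a power example: s = 1.1, 255 evaluable per arm, true GMR 1.25 and a lower limit above 1 give 63% unadjusted and 75% at r = 0.5. Every input is assumed. The 255 is 300 × 0.85, and the only 15% nonevaluable rate in the available text belongs to Substudy A. It should not be read as this trial's power.

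**Conclusion.** The point holds in a limited form. Section 9.3.1.2.3 does not correctly describe a ratio between independent randomised groups, and it leaves out two baseline variables that the trial has. For any randomised between-group GMR that this section governs, the cost is precision only: the interval could be narrower by nothing at r = 0, 5% at r = 0.3, 13% at r = 0.5 and 20% at r = 0.6. These figures assume a linear relation between baseline and post-dose log titre with the stated correlation, and they leave out any gain from the age stratum.

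A reader might infer that every randomised booster comparison in the protocol is widened. The documents do not support that: Substudies A, B and C list no between-group GMR, Substudy C already separates age groups, and the methods for D, E and F could not be checked. No stated number in the protocol is shown to be wrong.

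**What to change.** Split Section 9.3.1.2.3 in two.

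1. Within-participant ratios (for example two strains in one serum): keep the mean of the paired log differences with a one-sample t interval, and state the pairing.
2. Randomised between-group ratios: GMR = exp(difference in least-squares means) from a linear model for log titre with vaccine group, baseline log titre and randomisation age stratum (where more than one stratum is analysed together), with a model-based two-sided 95% CI. Report the unadjusted ratio, exp(difference of the two group log means) with a two-sample t interval, as a sensitivity analysis.

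If a substudy appendix already specifies an adjusted model, replace item 2 with a reference to it. First check Sections 10.10.9.3, 10.11.9.3 and 10.12.9.3 and the SAP.

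Cost: a short rewrite of one section and the matching SAP text, with no new data. The model spends one degree of freedom per added term and drops participants with no baseline titre, since Section 9.3.1 rules out imputing serology; report how many are dropped. Under Section 9, a major change to a primary endpoint analysis also needs a protocol amendment. The document is at amendment 12, and the sponsor is not blinded in Cohort 1, so the change should be dated before the comparative titres concerned are seen. Otherwise the adjusted result should be labelled supportive.
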